Participants will start by being administered the Expressive One-Word Vocabulary Test normed for ages 2 and older. Failure to score at least in the 15th percentile will lead to termination of participation, but with full payment of any honoraria. Preceding telephone or email screening will be designed to make such failure extremely unlikely. Special language and procedures will be designed and incorporated in the OHSU IRB information sheet to prevent any negative feelings due to termination.

In the design, usability and intelligibility portions of the study participants will interact with a computerized system, Audiobooks for HL App, in tasks that involve using audiobooks. The researcher will observe and take notes of any problems the subject encounters with the iPad. The subject can take breaks as needed by pausing the screen on the iPad. Then they will answer questions via a survey given by the researcher. This session will take 1- 2 hours and the subject will be paid \$20 regardless of whether the session is completed.

In the evaluation portion of the study participants will be given the BKB-SIN test for the first 6 weeks. Then, the study participants will also use the Audiobooks for HL App for the remaining 6 weeks using the App at least two hours per week total. The researcher will conduct 12 weekly remote visits via video conference where the following will be done:

- Throughout the 12 week study, the BKB-SIN will be administered using 2 new word list pairs in each session rotating through all 18 list pairs. The BKB-SIN is a speech-in-noise test that uses BKB (Bamford-Kowal-Bench) sentences, recorded in four-talker babble.
- During the last 6 weeks of the study the following will be done, in addition to the administration of the BKB-SIN.
- Observe the subject use the audiobook for 20-30 minutes.
- Conduct a comprehension test. Questions will be developed with the Sentence Verification Technique (SVT; Royer, 2001), in which alternative versions of passages in the materials are written and participants are to decide which version matches what was read. These questions (up to 5 per hour of read materials) will be presented in text form and answers will be recorded and scored during the session.
- Address any usability issues the participant brings up.

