The data will not be shared with the subjects because the research is still in an early phase and the reliability of the results is unknown.

c) Data Banking

All data will be stored for up to ten years for future analyses in this study. Access to data is restricted to study personnel. All of BioSpeech's study personnel are required to participate in a mandatory, ongoing training program on human subject protection. Hard copy data will be secured in a locked filing cabinet. Electronic data will be stored on restricted drives on the OHSU network as well as on the cloud file storage solution provided by Box.com.

8) Data Analysis

We will use a multiple baseline method. We will administer the BKB-SIN in 12 weekly sessions, using 2 new word list pairs in each session rotating through all 18 list pairs. In the training phase, starting in week #7, participants are asked to use the App at least 2 hours per week. To evaluate auditory training efficacy of the App we will measure the change in slope of the curve relating test performance to session number. This will be evaluated by computing for each subject, S , a normalized slope difference, $ZS = (bs_1 - bs_2) / \sqrt{SE_{bs_1}^2 + SE_{bs_2}^2}$; here, $j=1,2$ refers to pre- and in-training phase, and, for each subject S , bs_j 's are the associated slopes and SE_{bs_j} 's the standard errors of the slopes.

The design of the study allows for multiple statistical analyses. We will conduct analysis within-subjects, as noted above. We will also conduct planned comparisons between selected groups, using t -tests, comparing score changes between a pre-post change.

Since ZS is approximately normal, we apply a one-tailed single-sample t -test to the 40 ZS 's, yielding a power of 0.80 at $p=0.05$ (one-tailed) for small-medium effect sizes ($d=0.4$).

9) Privacy, Confidentiality and Data Security

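### The plan does not require BKB-SIN list order to differ between participants; under one common order with unequal lists, the slope-change test can exceed its 5% error rate

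*Combined protocol and SAP*

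**What the plan says.** Section 6 (Procedures) states that "the BKB-SIN will be administered using 2 new word list pairs in each session rotating through all 18 list pairs", and section 8 (Data Analysis) repeats the rule: "using 2 new word list pairs in each session rotating through all 18 list pairs". No other rule on lists is given. Neither section mentions a starting pair, randomisation or counterbalancing of order, or the equivalence of the list pairs.

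The timetable is the same for everyone. Section 6 says "participants will be given the BKB-SIN test for the first 6 weeks", and section 8 places the change of phase at a fixed point: "In the training phase, starting in week #7". The design is called multiple baseline, but the start of training is not staggered and there is no untrained comparison arm.

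The outcome is the "change in slope of the curve relating test performance to session number". Each participant's slope difference is divided by its standard error to give ZS, and "we apply a one-tailed single-sample t -test to the 40 ZS 's". Section 8 attaches a one-tailed 0.05 level and a power of 0.80 to this test. The model for ZS contains session number only, with no list term.

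**The concern.** The rule can be followed to the letter by giving all 40 participants the same pairs in the same session. List difficulty and session number would then be completely aligned in sessions 1 to 9. Any unevenness between lists would become a fixed pattern over sessions 1–6 and 7–12, and that pattern would enter every participant's slope difference with the same sign and size.

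The t-test judges the mean ZS against the spread between participants. A shift common to all moves the mean without widening that spread, so the test cannot detect it and more participants do not dilute it. With no comparison arm and no staggered start, nothing else in the design would separate it from an App effect. At stake is the only test in the plan with a stated significance level: it could credit the App with a list effect, or lose a real App effect behind one.

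**Working it through.** **Inputs from the documents.** 40 participants; 12 sessions; 2 list pairs per session from 18; phases of sessions 1–6 and 7–12; one-tailed test at 0.05; d = 0.4 and power 0.80 (sections 6 and 8).

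**Inputs assumed.** Session-score noise has SD 1 and is independent. List-pair difficulty has SD s, in units of that noise, varied from 0 to 0.5. There is no App effect on average.

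**The plan's own figure.** One-sample t-test, df 39, noncentrality 0.4 × √40 = 2.530: exact one-tailed power is 0.7997. The stated 0.80 is reproduced. It presumes that the 40 values carry no shared error.

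**Size of the shared shift under one common rotation.**

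1. In each phase the centred session numbers are −2.5, −1.5, −0.5, 0.5, 1.5, 2.5, with sum of squares 17.5.
2. Two pairs per session make nine sets. Sets 1–9 fall in sessions 1–9, and sets 1–3 return in sessions 10–12.
3. In (first slope − second slope) × 17.5, the nine sets have weights −3, −3, −3, 0.5, 1.5, 2.5, 2.5, 1.5, 0.5. Their squares sum to 27 + 17.5 = 44.5.
4. A set is the mean of two pairs, so its variance is s²/2. The shared shift therefore has SD √(44.5/17.5² × s²/2) = 0.2695 s.
5. One person's slope difference has sampling SD √(2/17.5) = 0.338, so the mean of 40 has SE 0.338/√40 = 0.0535.
6. With k = 0.2695 s / 0.0535, upper-tail rejection averaged over possible list difficulties is approximately 1 − Φ(1.645/√(1 + k²)).

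Example, s = 0.2: k = 0.0539/0.0535 = 1.009, and 1.645/1.420 = 1.158, which gives 12.3%.

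**Allowing real differences between people.** If true slope changes have mean zero and SD 0.34, about the size of the sampling SD, the SE becomes √((0.338² + 0.34²)/40) = 0.0758, and k falls accordingly.

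This approximation works on the slope difference before division by its standard error. Simulations of the actual ZS and t-test (3,000 to 4,000 null trials per setting in the runs whose size was recorded) agree with it:

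| List-pair SD s | Approximation, no variation between people | Simulated ZS test | Approximation, slope-change SD 0.34 | Simulated ZS test |
|---|---|---|---|---|
| 0 | 5.0% | about 5% | 5.0% | about 5% |
| 0.1 | 7.1% | 6–7% | 6.1% | about 6% |
| 0.2 | 12.3% | 10–12% | 9.0% | 8–9% |
| 0.3 | 18.2% | 16–18% | 13.0% | 12–14% |
| 0.5 | 27.2% | 24–27% | 21.0% | 19–21% |

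The lower tail is inflated about equally.

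**Scale.** If the SD of 1 is attached to a single list-pair score, the session mean has noise 1/√2 = 0.707. The simulated rates without variation between people then rise to about 9%, 17%, 23% and 32% for s = 0.1, 0.2, 0.3 and 0.5.

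**Order varied by participant.** With a different starting pair per person, or a random permutation per person, simulated rejection stays between about 4% and 6% over the same range of s.

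**The case against.** The strongest reply is that the documents are silent on order across participants. Rotation is as compatible with a different starting pair for each person as with one sequence for all, and with varied starts the error stays near 5%. A reader might infer that all 40 participants do share one sequence, or that the error rate is certainly no longer 5%. The text supports neither statement.

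Three further points stand. First, inflation needs list pairs that differ in difficulty. The documents give no figure, and at s = 0 there is none. Second, a model with independent noise only is the less favourable case. The trial deliberately mixes five diverse subgroups, and real variation in slope change reduces the inflation, though it does not remove it. Third, the percentages are averages over possible list difficulties. One actual set of lists in one order has its own fixed bias, which could favour the App, oppose it or be negligible.

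The silence does not dispose of the point. The only rule given permits the harmful arrangement and does not require the sound one. Nor could a common order be cleanly repaired in the analysis: pairs 7–18 each occur in a single session (sessions 4–9), so a list term there could not be told apart from session.

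**Conclusion.** The concern holds as a conditional one. The plan leaves list order across participants open and has no list term. If one common rotation is used and list pairs are unequal, the one-tailed type I error of the t-test on ZS exceeds 5%. The excess is slight when list differences are a tenth of session noise. At half of session noise the error reaches 24–27%, or 19–21% with slope-change SD 0.34 between people. Both SDs are assumptions, because the documents give neither. Since both tails are affected, a fixed order could produce a false benefit or mask a true one. That the trial actually runs one common order, or that its lists are unequal, is not established.

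**What to change.** State in sections 6 and 8 that each participant has a pre-generated list order, and record the list pairs used at each session. Two forms would serve:

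- a random permutation of the 18 pairs per participant; or
- the nine starting positions spread as evenly as possible over the 40 participants and over the subgroups. Exact balance is impossible: there are 8 people per subgroup for nine starts, and 40 = 9 × 4 + 4, so four starts would be used five times and five starts four times.

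The cost is one order sheet per participant and a sentence in each section, with no added sessions, tests or participants. If varied orders are already intended, those sentences settle the point.

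This does not deal with list reuse. The schedule needs 12 × 2 = 24 list-pair slots and has 18 pairs, so under straight rotation sessions 10–12 repeat six pairs, which contradicts the wording that each session's pairs are new. All the repeats fall in the training phase for everyone, whatever the order, so that conflict must be reconciled separately.
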